#### Effective contraception include:

- True abstinence: when this is in line with the preferred and usual lifestyle of the subject (Periodic abstinence, e.g. calendar, ovulation, symptothermal, post-ovulation methods, declaration of abstinence for the duration of the trial, and withdrawal are not acceptable methods of contraception)
- Male partner vasectomy or other medical condition causing azoospermia
- Male partner using condom
- Intrauterine device
- Female barrier method (cervical cap or diaphragm with spermicidal agent)
- Tubal sterilisation
- Levonorgestrel implant
- Injectable progesterone
- Oral contraceptive (combined or progesterone only)
- Contraceptive vaginal ring
- Transdermal contraceptive patch

## 13.0 Trial Procedures

#### 13.1 Recruitment

#### 13.2 Participant identification

Within the NHS HCV treatment delivery pathway, all treatment centres in England are arranged in networks according to geographical regions, with a centre lead or 'hub' which coordinates treatment decisions via multidisciplinary team (MDT) meetings. All sites within the study are approved centre leads for London, thus facilitating participant identification and recruitment. In accordance with European guidelines, NHS England mandates that all patients receiving NHS funded therapy undergo viral load testing after 2 weeks of treatment. Recruiting centres will monitor all potentially eligible patients who have initiated antiviral therapy and those who are viraemic after 2 weeks will be contacted by their treating centre and asked to consider enrolment in the study. Those who agree to consider the trial will be provided with the patient information sheet and offered an opportunity to discuss the trial with the study team. Those who agree to participate will sign the informed consent form and then undergo screening prior to enrolment in the trial.

#### 13.3 Informed Consent Procedures

Informed consent must be obtained prior to the participant undergoing procedures that are specifically for the purposes of the trial and are outside standard routine care at the participating site (including the collection of identifiable participant data).

#### 13.3.1 Responsibility for obtaining consent

The Principal Investigator (PI) retains overall responsibility for the informed consent of participants at their site and must ensure that any person delegated responsibility to participate in the informed consent process is duly authorised, trained and competent to participate according to the ethically approved protocol, principles of Good Clinical Practice (GCP) and Declaration of Helsinki. If delegation of consent occurs then details should be provided in the Site Delegation Log.

Consent should be taken by a doctor within the study.

#### 13.3.2 Consent Considerations

The right of a participant to refuse participation without giving reasons will be respected.

The participant must remain free to withdraw at any time from the trial without giving reasons and without prejudicing his/her further treatment and must be provided with a contact point where he/she may obtain further information about the trial. Where a participant is required to re-consent, for example if during the trial new Research Safety Information becomes available, or following an amendment that affects the patient, or new information needs to be provided to a participant, it is the responsibility of the PI to ensure this is done in a timely manner.

#### 13.3.3 Population

The study population is of patients chronically infected with genotype 3 HCV and compensated or decompensated cirrhosis. Subjects are selected based on poor predicted response to treatment with sofosbuvir/velpatasvir (on the NHS programme), defined by persistence of HCV (≥30 iu/mL) in patient serum after 2 weeks (+/-3 days) of therapy.

#### 13.3.4 Vulnerable participant's considerations

NA

#### 13.3.5 Written/reading/translation considerations

Owing to the ethnic diversity of London, significant number of participants who cannot read or write in English, or cannot read or write at all, may be involved in this study. This is particularly as genotype 3 HCV is common amongst South Asians. It would be impractical for this study to make available translated versions of study documents in many languages. Instead, the study requires that oral translation is available to facilitate consent, e.g. via telephone translator service, hospital translator, or an impartial translator who is not part of the study (family members should not be used for consenting). The translator will sign the consent form as well as the participant. Where a telephone service is used, the investigator will sign that translation has taken place to facilitate consent. Where participants cannot sign consent, such as due to lack of written language, an impartial witness (such as the translator) can sign on their behalf.

## 13.3.6 Participants lacking capacity

This study excludes participants unable to provide informed consent. Conditions such as severe psychiatric illness or hepatic encephalopathy, or participants under influence of alcohol or illicit drugs which impair their capacity to consent, are excluded. This is at the discretion of investigators to judge.

13.3.7 Minors

NA

## 13.3.8 Consenting process

The investigator is responsible for obtaining written informed consent from each participant after adequate explanation of the study aims, methods, and possible risks. Patient Information Sheet and consent form approved by REC and in compliance with GCP, local regulatory requirements and legal requirements should be provided. The investigator who is taking consent is responsible for assessing the capacity of the participant to sign informed consent.

Patients deemed suitable for the study by their treating physician will be asked to consider participating. Those willing to consider participating in the study will be provided with a Patient Information Sheet. Participants must be allowed opportunities for questions and at least 24 hours to consider their participation. The date that the Patient Information Sheet is given to the participant must be documented within the medical notes to ensure that sufficient time is given. If for any reason, less than 24 hours is given, the justification for this should be documented.

13.3.9 Additional consent provisions for collection and use of participant data and biological specimens in ancillary studies

None

## 13.4 Screening Procedures

Following consent, participants are screened for inclusion/exclusion criteria. All participants who undergo screening should be logged and the investigator who performed this assessment should be documented.

Screening takes place between treatment week 8 up to end of treatment week 12. Sites must ensure that there is sufficient time between screening and end of week 12 treatment for additional IMP dispensing for participants randomised to arm B (24 weeks treatment), such that there is no interruption in study drug supply.

Review of clinical records for eligibility

- Anti-HCV antibody or HCV RNA detection for greater than 6 months before screening
- HCV genotype 3

- Document pre-treatment HCV viral load must be >10,000 iu/mL (use last result at any time before treatment week 0)
- Commenced NHS treatment with sofosbuvir/velpatasvir
- Document date and result of HCV RNA at treatment week 2 (+/- 3 days) must be detectable HCV (≥30 iu/mL, Roche TaqMan quantitative test, or other validated methods)
- Document criteria for determining cirrhosis (evidence of portal hypertension, OR APRI >2 plus AST:ALT ratio >1, OR radiological evidence of cirrhosis, OR fibroscan score >11.5kPa, OR liver biopsy showing cirrhosis)
- Document presence (or history of) decompensation (variceal bleeding, ascites and encephalopathy)
- Any liver imaging (e.g. USS/CT/MRI) within 6 months of treatment week 0 to document presence of hepatocellular carcinoma
- Document previous history of hepatocellular carcinoma or other malignancy
- Document if co-infected with chronic hepatitis B virus (HBsAg) or HIV (antibody)
- Document complete medical, surgical and psychiatric history, and investigator assessment of suitability for trial enrolment
- Baseline eGFR (within 3 months of treatment week 0) must be >30 ml/hr and patient not requiring dialysis
- Current alcohol and illicit drug use if positive history, document whether investigator deems participant suitable
- Document previous hepatitis C treatment history (pegylated interferon, ribavirin, DAA, trial medication), response to treatment and any adverse events or intolerances
- No previous exposure to sofosbuvir (or other NS5B inhibitor) or NS5A inhibitor
- Document complete drug history see Exclusions for list of prohibited concomitant medications.
- Document allergies
- Document if any investigational medicinal product ≤ 6 weeks prior to treatment start
- Document participant is not a pregnant or nursing female, or wishing to conceive during the study treatment period + 30 days after
- Document adherence to sofosbuvir/velpatasvir (reported number of missed pills) from treatment week 0 (NHS programme) to screening date – participants must have at least 90% adherence

Document contraception and breast-feeding advice, and currently in use or chosen method of protocol-specified contraception (if applicable)

Examination to assess eligibility (must be performed by study doctor)

- Physical examination cardiovascular, respiratory, gastrointestinal, others as deemed appropriate by study doctor
- Document if any active decompensation

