#### 12.2 Exclusion Criteria

- Any of the above inclusion criteria not met
- Any of the following criteria excludes a subject from enrolling into this study
- Clinically-significant medical or psychiatric illness (other than chronic HCV) in the past, present, or being evaluated, that may interfere with participant treatment, safety, assessment or compliance with the protocol.
- Severe renal impairment with eGFR <30 mL/min/1.73m^2 or requiring dialysis
- Alcohol consumption or illicit drug abuse likely to interfere with participant treatment, safety, assessment or compliance with protocol, as deemed by the investigator
- Previous exposure to sofosbuvir (or other NS5B inhibitor) or NS5A inhibitor
- Severe allergy to study drugs, its metabolites or formulation excipient (see SmPC for details)
- Any investigational medicinal product ≤ 6 weeks prior to treatment start
- Pregnant or nursing female, or males wishing to conceive during the period of study treatment + 30 days after
- Patients who adhered to less than 90% of prescribed sofosbuvir/velpatasvir at screening
- In accordance with the SmPC of sofosbuvir/velpatasvir concomitant use of the following medications are contraindicated:

Anticonvulsants - carbamazepine, phenytoin, phenobarbital, oxcarbazepine

Antimycobacterials - rifampicin, rifabutin, rifapentine

Antiretrovirals - efavirenz

St John's wort

Modafinil

Proton-pump inhibitors should be avoided and if necessary, should be administered 4 hours after at maximum doses equivalent to 20mg omeprazole per day.

Amiodarone should be avoided and if necessary, close monitoring is required

Please consult the SmPC and Section 15.16 and 17 for list of medications to be used with caution or monitoring.

Participants taking these medications must have discontinued prior to starting sofosbuvir/velpatasvir (this is expected to be in line with standard care practice). Definition of child-bearing potential and effective contraception:

Subjects are considered not of child-bearing potential if they are surgically sterile (undergone a hysterectomy, bilateral tubal ligation, or bilateral oophorectomy) or they are postmenopausal (women aged  $\geq$  45 years of age with cessation of previously occurring menses for  $\geq$  12 months) or they have medically-documented ovarian failure.

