#### Tests

check for negative urine b-HCG for females of child-bearing potential

Record baseline laboratory tests (within 3 months of treatment week 0) and date of tests: haemoglobin, platelets, bilirubin (total), alanine transaminase (ALT) albumin, creatinine, eGFR (Cockcroft-gault or MDRD formula)

A log of participants who are screened but not randomised should be documented. For CONSORT reporting, those not randomised should have demographic data (age, gender, ethnicity), whether enrolled, documented. The reason for not undergoing randomisation should be documented.

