#### 13.5 Patient Allocation

#### 13.5.1 Randomisation Method

Participants who fulfill inclusion/ exclusion criteria will be randomised. This takes place anytime after enrolment between treatment week 8 to 12. Sites must ensure sufficient time to randomise participants and dispense additional IMP for those in the arm B (24 weeks) such that there will not be more than 24 hours before commencing week 13 treatment.

Participants will be allocated into treatment arms A and B in a 1:1 ratio, by block randomisation, and stratified by whether they have compensated cirrhosis or decompensated cirrhosis at baseline. Participants with previous history of decompensation will be considered as having decompensated cirrhosis for the purpose of stratification. This is in order to generate equal numbers within each arm, with balanced severity of liver disease distributed. Clinical trial data suggests that severity of liver disease and presence of decompensated cirrhosis are one of the most important factors determining treatment outcome [8].

There may be other patient factors which influence treatment success, but further stratification for a study of 60 participants would not be appropriate. Block randomisation will enable interim analysis to be performed with balanced groups.

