13.8 Trial Schedule

13.8.1 Schedule of Treatment for each visit

13.8.2 Schedule of Assessment (in Diagramatic Format)

Study Visits Schedule for Arm A – 12 weeks of sofosbuvir/velpatasvir							
	Treatment week	0-8	8-12	12	16	20	24
	Visit windows			+/- 7 days	+/- 14 days	+/- 14 days	+ 28 days
Assessments		Pre-	Screening/	End of	Post	Post	End of
		enrolment	baseline	treatment	treatment	treatment	study
NHS treatment visits		х					
Informed consent			х				
Review inclusion/exclusions	Supply participant card		х				
Randomisation			х				
Pregnancy test (if applicable)	Urine test		х				
Document contraception/ breastfeeding advice (if applicable)			х	х	х		
Record demographics			х				
History			х				
Physical examination	Cardiovascular		Х				
	Respiratory		X				
	Gastrointestinal		X				
Review concomitant medications			X	х			
Prescription and dispensing of NHS treatment		х					
Prescription and dispensing study drugs							
Drug accountability	Record missed doses		х	х			
Adverse events recording	Events since week 0		х				
C	Events since last visit			x	x	x	x
Laboratory samples	FBC			Х	Х	Х	Х
	Urea & electrolytes,			Х	Х	X	Х
	creatinine			Х	Х	X	X
	LFTs			Х	Х	X	X
	Albumin			Х	x	x	X
	HCV RNA			Х	(optional)	(optional)	Х
Quality of life questionnaire				x			x

Study Visits Schedule for Arm B – 24 weeks of sofosbuvir/velpatasvir							
	Treatment week	0-8	8-12	12	16	20	24
	Visit windows			+/- 7 days	+/- 7 days	+/- 7 days	+/- 7 days
Assessments		Pre-	Screening/	Study	Study	Study	End of
		enrolment	baseline	treatment	treatment	treatment	treatment
NHS treatment visits		х					
Informed consent			х				
Review inclusion/exclusions	Supply participant card		х				
Randomisation			х				
Pregnancy test (if applicable)	Urine test		х				
Document contraception/			х	х	х	X	Х
breastfeeding advice (if applicable)							
Record demographics			х				
History			х				
Physical examination	Cardiovascular		X				
	Respiratory		X				
	Gastrointestinal		X				
Review concomitant medications			X	х	X	X	X
Prescription and dispensing of NHS		x					
treatment							
Prescription and dispensing study				Х	Х	X	Х
drugs							
Drug accountability	Record missed doses		х	х	Х	X	Х
Adverse events recording	Events since week 0		x				
	Events since last visit			х	х	х	х
Laboratory samples	FBC			X	X	X	X
	Urea & electrolytes,			Х	Х	X	Х
	creatinine			X	Х	X	Х
	LFTs			X	Х	X	Х
	Albumin			x	x	x	Х
	HCV RNA			(optional)	(optional)	(optional)	х
Quality of life questionnaire							X

	Treatment week	28	32	36

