#### Determine inclusion / exclusion criteria

- document genotype, baseline HCV viral load and date(last result prior to treatment week 0, must be >10,000 iu/mL to be eligible), HCV viral load at treatment week 2 (+/-3 days)
- document criteria used to determine cirrhosis or decompensated cirrhosis from clinical records
- document any imaging (e.g. ultrasound / CT / MRI, with dates ) within 6 month before treatment start, if available – to determine presence of hepatocellular carcinoma
- document hepatitis B virus and HIV status
- for females of child-bearing potential only urinary pregnancy test negative
- document contraception and breast-feeding advice in the medical records
- document complete medical, surgical and psychiatric history and study doctor assessment of whether subject is eligible
- document baseline (within 3 months of treatment week 0) laboratory tests eGFR must be
   >30ml/hr and patient not requiring dialysis
- document alcohol and illicit drug use and study doctor assessment of whether subject is eligible

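### The renal exclusion is verified at screening (treatment weeks 8-12) on an eGFR dated to week 0, so an unmeasured fall below the limit could pass before randomisation (minor)

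*Protocol*

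**What the plan says.** Section 12.2 excludes "Severe renal impairment with eGFR <30 mL/min"/1.73m2, or need for dialysis, and attaches no date. Section 15.2 gives the reason: the drugs are not licensed in that population.

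The working instructions are narrower. Section 13.4 says "Baseline eGFR (within 3 months of treatment week 0) must be >30 ml/hr and patient not requiring dialysis". Section 13.8.3, under the inclusion and exclusion checks, repeats the window: "document baseline (within 3 months of treatment week 0) laboratory tests eGFR must be" above 30. Under Tests in section 13.4, the site is told to "Record baseline laboratory tests (within 3 months of treatment week 0) and date of tests". The one test to be performed there is the pregnancy test: "check for negative urine b-HCG for females of child-bearing potential". The examination part of 13.4 does look at current state for liver function: "Document if any active decompensation".

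In section 13.8.2, neither the Arm A table nor the one headed "Study Visits Schedule for Arm B" marks any laboratory sample in the week 8-12 column. The first trial creatinine is at the week-12 visit (+/- 7 days). In Arm B this is also the first dispensing visit (13.8.3). Randomisation must come before the last week-12 dose (13.8.3, Study assessments), and supply must be arranged "such that there will not be more than 24 hours before commencing week 13 treatment" (13.5.1).

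**The concern.** Eligibility is decided at weeks 8-12, but the renal value used to decide it describes the patient at or before week 0. Other criteria that can change during treatment are looked at when the patient is screened: active decompensation, adherence, pregnancy, and alcohol or drug use. Renal function is not.

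The population makes a change plausible. Section 12.1 admits decompensated cirrhosis, liver transplant and HIV co-infection, and section 15.17 allows tenofovir with caution. Weeks 13-24 are the exposure that the trial itself adds. A patient whose eGFR has fallen below 30 without anyone measuring it can satisfy the instructions in 13.4 and 13.8.3 and be randomised, although 12.2 and 15.2 mean to keep that patient out.

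**Working it through.** The protocol states no figure for this point, so there is none to reproduce. The check is date arithmetic and a comparison of sections.

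**Age of the qualifying eGFR.** Inputs: a window of 3 months around week 0 (13.4, 13.8.3), screening at weeks 8 to 12 (13.4), first extension dose after week 12 (15.1). Three months = 365.25/12 × 3/7 = 13.04 weeks, taken as 13.

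| Sample drawn | Age at screening | Age at first extension dose |
|---|---|---|
| Day 0 | 0 + 8 = 8 to 0 + 12 = 12 weeks | 12 weeks |
| 13 weeks before day 0 | 13 + 8 = 21 to 13 + 12 = 25 weeks | 25 weeks |

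If the window is read as running on both sides of week 0, an on-treatment value is allowed but still not required.

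**When the trial first measures creatinine.** With treatment start as day 0, week 12 is day 12 × 7 = 84. The visit window is 84 − 7 = day 77 to 84 + 7 = day 91. For a patient screened late, a sample taken early in that window could precede randomisation. Nothing requires this, and for a patient randomised at week 8 it cannot happen. No section ties randomisation or first dispensing to the result.

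**Where the limit is stated.**

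| Place | Rule | Unit | Date attached |
|---|---|---|---|
| 12.2 | <30 excluded | mL/min/1.73m2 | none |
| 13.4 | >30 required | ml/hr | within 3 months of week 0 |
| 13.8.3, inclusion/exclusion checks | >30 required | ml/hr | within 3 months of week 0 |
| 13.8.3, list of baseline results | <30 excluded | ml/hr | list is dated; the note itself is not |
| 15.2 | <30 excluded | ml/hr | none |

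Four of the five statements carry the wrong unit; read literally, 30 mL/hr is 30/60 = 0.5 mL/min. Three exclude values below 30 and two require values above 30, so a value of exactly 30 passes in three places and fails in two.

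**Effect of a check placed after randomisation.** Section 19.5 counts a 24-week participant only if at least one extension dose was taken. If dispensing in Arm B were blocked on the week-12 creatinine, those patients would leave the primary analysis, while Arm A patients with the same fall would stay in. A check that decides eligibility therefore belongs before randomisation and in both arms.

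**The case against.** The strongest reply is that the governing rule is sound. Section 12.2 is undated, 13.8.3 repeats the exclusion and makes the study doctor judge eligibility, and screening includes a full history, an examination and a record of adverse events since week 0. Section 14.2 lists creatinine and eGFR among the laboratory data, though it names no visit. Creatinine is drawn at weeks 12, 16, 20 and 24 in Arm B, and the investigator may stop drug for clinical reasons (13.9). Every participant has already taken the same tablet for at least 8 weeks. Section 19.2 describes study requirements as similar to routine NHS treatment, so a recent NHS creatinine may often exist. The IMP Manual and laboratory manuals, which are not shown, might add a dispensing check.

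Most of this stands, and it keeps the point small. It does not close the gap. The undated rule and the doctor's judgement catch only a fall that is already known, and no section requires an NHS on-treatment result to be used.

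Three stronger readings are tempting and are not supported:

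- **That the protocol lets sites knowingly enrol patients below the limit.** Section 12.2 forbids it.
- **That unlicensed exposure would be substantial.** Added exposure is probably limited to the days until the week-12 result is read. The protocol gives no laboratory turnaround, and patients may finish leftover NHS tablets first, so neither a tablet count nor a latest start day can be fixed.
- **That the unit error moves the threshold 60-fold in practice.** Section 12.2 has the correct unit, and eGFR is not reported per hour.

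**Conclusion.** The point holds as a minor safety and eligibility gap. Sections 13.4 and 13.8.3 verify the renal limit on a value that may be 8 to about 25 weeks old at screening, and an unmeasured fall need not be detected before randomisation. The upper end needs a sample at the far edge of the window and no later NHS result. How often that happens is not stated, so no number of patients or tablets is given.

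The sample size and the definition of the primary endpoint are unaffected. A reader might infer that the efficacy comparison is at risk; it is not under the current text, and would be touched only by a renal check confined to Arm B after randomisation. The unit and boundary inconsistencies are editorial, but they sit in the text that sites use to check eligibility.

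**What to change.** - **Sections 13.4 and 13.8.3:** before randomisation and in both arms, apply the 12.2 criterion (eGFR <30 mL/min/1.73m2 excluded, ≥30 eligible) to the most recent on-treatment creatinine or eGFR, using a routine NHS result where one exists.
- **Week 12:** keep the scheduled sample in both arms, so that the Arm A end-of-treatment value is not lost. Have the investigator read the Arm B result as a safety check at first dispensing.
- **Section 19.5, and the matching sentence in 11.1:** state that a participant stopped on that result stays in the primary analysis as randomised, including one who took no extension dose.
- **Units and boundary:** replace ml/hr with mL/min/1.73m2 in 13.4, in both places in 13.8.3 and in 15.2, and use the one boundary throughout.

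The cost is a wording amendment, occasionally a blood result obtained earlier than now, and a rare extra exclusion. No scheduled sample is removed.
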